#### **5.5.B. Data Collection Strategy § 5.1.H.**

#### **5.5.C. Study Variables § 5.1.I.**

### **5.6 Data Analysis**

#### **5.6.A. Sample Size Calculation/Sample size determination**

Sample size is calculated according to the estimated intervention effect size at post-intervention. We then estimate power to detect treatment effects at the post-maintenance (10-month) follow-up as well as power to detect treatment differences in linear change across the three time points for a 3-level cluster-randomized trial with repeated assessments. We will adjust models for baseline covariates of study patients. All tests will be two-sided with an alpha of 0.05. In our recent RCT, differences in HbA1c change between EPIC versus enhanced group education indicated medium treatment effects at post-treatment and at 1-year (Cohen's  $d = 0.48$  and  $0.42$ , respectively). A similar trial revealed a treatment difference between a glucose self-monitoring protocol and an active control group in DDS scores that correspond to large effects of treatment at 1-year (all pre-post  $d$ s  $> 0.80$ ). To capture treatment effects for both clinical and patient centered outcomes in this implementation trial, a conservative small-to-medium effect size of  $d = 0.40$  (which is 16.67% smaller than the effect found for HbA1c in the prior trial) was used to calculate sample size. Assuming no intra-class correlation (ICC) within

PACTs, 100 patients in each treatment arm (i.e., EPIC and EUC) will allow for 80% power to detect small-to-medium effects and 98% power to detect medium effects ( $d = 0.50$ ). To account for the dependency among patients within a PACT, the Design Effect (Deff) was applied, following the approach of Schnurr et al. The sample size was inflated using the formula,  $Deff = 1 + (n-1)\rho$ , where  $n$  is the average number of patients per PACT and  $\rho$  is the ICC for PACTs. In our preliminary work, we identified an ICC for PACTs of 0.0183, an average of 27 eligible patients per PACT, and expect that an average of 12 patients per PACT will participate, which yields  $Deff = 1 + (12-1) * 0.0183 = 1.2013$ . Applying this adjustment, the minimum number of patients in the clustered design is  $100 \times 1.2013 = 120$  in each treatment group. Further adjusting for a maximum of 15% attrition, 142 patients will be recruited for each treatment group (total  $N = 284$ ). Therefore, the minimum number of PACTs to be sampled for this nested analysis is technically 11.8, (i.e.,  $142/12$ ), which will be rounded up to 24 PACTS. This is highly feasible, representing just 32.5% of the total number of PACTs (75) at all study sites. Treatment group effect sizes as small as  $d = .40$  can be detected with 80% power at 1-year given a total of 284 patients (an average of approximately 12 patients randomized to either EPIC or EUC from within 24 PACTs sampled), even after accounting for maximum attrition and estimated dependency within PACTs. A sample size of 284 participants is adequate for repeated measures analyses as well. Optimal design software estimated power to detect treatment group differences in linear change across all three assessments. Prior data indicated a main effect of treatment (EPIC versus enhanced group education) for linear change in HbA1c of 0.20, and between – and within – PACT variance in linear change of 0.018 and 0.206, respectively. These values indicate a small-to-medium between-groups effect size of 0.42. A total of 284 participants allows for 80% power to detect a slightly larger effect size ( $\delta = .53$ ) for repeated measures analyses of linear change over time. Furthermore, there is 98% power to detect a medium effect size of  $\delta = .75$ .

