### **5.1.I. Study Variables**

**5.1.I.a. Screening Interview.** The screening interview will be conducted over the phone and will identify exclusionary variables by self-report that would render participation in a group clinic inappropriate: 1. Substantial hearing or vision loss, such that participation with the materials and group exercises would not be possible. 2. Transportation or availability barriers, such that would prevent the participant from presenting in person on a regular basis. 3. Unwillingness to discuss their health and health care in a peer-group setting. 4. Cognitive functioning. Cognitive functioning will be assessed using a six-item screening tool that has been validated for telephone use. 5. Current active substance abuse. We will administer modules from the MINI, a short structured interview used to identify mental health conditions including substance abuse according to DSM-IV. It is appropriate for telephone screening (Attachment 9 and 10).

**5.1.I.b. Primary Outcomes.** **1. Diabetes Control Measure.** HbA1c is an established measure of diabetes control and a strong predictor of subsequent health outcomes related to diabetes. There is consensus that levels  $>7\%$  should be treated because of their association with both cardiovascular risk and microvascular end-organ damage (e.g., kidney failure). Our eligibility criteria of HbA1c of  $\geq 8\%$  at baseline allows for detection of a clinically significant change without limiting enrollment to only those with very poor control or other selective groups. **2. Diabetes-related Distress Scale (DDS).** DDS, a 17-item instrument that assesses psychological burden specific to diabetes care (see Attachments 7, 8, and 11), has high internal consistency, reliability ( $\alpha = 0.93$ ) and validity with self-care behaviors ( $r = .30, P < .001$ ) and physical activity ( $r = .13, P < .01$ ). DDS scores correlate with HbA1c levels and are a robust measure of other clinically significant diabetes self-management endpoints. Phase 2 study measures and the data collection timeline are outlined in Table 10.

**5.1.I.c. Baseline Covariates.** **1. Patient-Level Characteristics (Self-report):** We will collect date of birth, gender, race, education, living situation [alone or not], social support, VA

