Specific Aim 2: The distributional nature of all variables will be assessed, and nonparametric tests (e.g., Fisher's Exact Test; Mann-Whitney test), data transformations (e.g., log linear), or other alternate methods (e.g., weighted least squares regressions) will be conducted where appropriate. First, we will compare baseline demographic, clinical, and patient-centered variables (including medication use) between EPIC and EUC with chi-square and independent samples t-tests. Variables with p-values  $< 0.25$  will be included as control variables or propensity scores in subsequent models. We will then compare baseline demographic, clinical, and patient-centered variables between those who complete the study and those who do not using chi-square and independent samples t-tests. Outcome analyses at both post-intervention and post-maintenance will be intention-to-treat and will use the multiple imputation procedures Proc MI and MINANALYZE in SAS Version 9.3 to estimate missing observations. We will evaluate the degree of dependency between patients within a given group session, between patients in a given PACT, and between PACTs within each of the five sites (by examining Intra Class Coefficients). It is likely that significant dependency will exist, and if so, we will accordingly take these into account in analyses (i.e., patients will be nested within PACTs which will in turn be nested within sites). Random regression methods using SAS Proc Mixed will be employed to account for clustering of data.

5.6.C.i. H2 Analyses (Effectiveness) We will employ Analysis of Covariance (ANCOVA) to examine treatment differences in outcomes immediately post-intervention (at 4 months). We will conduct two models: one with HbA1c at post-intervention as the outcome and one with DDS at post-intervention as the outcome. Models will include treatment group (i.e., EPIC versus EUC) as a predictor and respective HbA1c and DDS baseline scores and any demographic,

clinical, or patient-centered variables that differed between the study arms at baseline as covariates. We will calculate treatment effect sizes immediately post-intervention.

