5.6.C.ii. H3 Analyses (Maintenance) Analyses for examination of maintenance of treatment effects will be similar to those for immediate treatment effects post-intervention. We will again employ ANCOVA to examine treatment differences in outcomes at the post-maintenance (10-month) assessment. We will conduct two models: one with HbA1c at 10-months as the outcome and one with DDS at 10-months as the outcome. Models will include treatment group (EPIC versus EUC) as a predictor and respective HbA1c and DDS post-intervention scores and any demographic, clinical, or patient-centered variables that differed between the study arms at baseline as covariates. We will calculate treatment effect sizes at the 10-month assessment.

5.6.C.iii. Exploratory Analyses (Implementation and Effectiveness) We will use a mixed-model approach to conduct separate repeated-measures analyses for HbA1c and DDS simultaneously using all three assessment time points. We will employ growth curve analyses using SAS Proc Mixed to examine overall group differences in improvements or decrements in outcomes over the year, maximize participant data, and account for dependency between patients within a given group session, PACT, and site. Conditional models will contain fixed terms for the intercept, treatment (EPIC or EUC), assessment time period, treatment by time period interaction, and previously identified variables that differ between treatment groups. Modeled random effects will include between-patient variation in baseline scores (i.e., the intercept where baseline assessments are scored 0) and variation in the slopes for time. With three assessments, the focus will initially be on linear patterns of change, although we will evaluate the relative fit of a quadratic pattern of change using the likelihood ratio test. These analyses will allow us to examine the immediate impact of treatment at post-intervention as well as retention, improvement, or decay in outcomes post-maintenance period. The treatment effect will assess differences between the two groups at baseline, the fixed effect of time will measure the average change over time in the outcome (collapsing across the two treatment groups), and the time by treatment interaction will indicate whether change over time (in slopes) differs between EPIC and EUC.

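### HbA1c and DDS are unranked primary outcomes, each tested at 0.05 post-intervention with no success rule; if either suffices, the family-wise error is about 9–10%, not 5%

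*Combined protocol and SAP*

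**What the plan says.** Section 5.1.I.b puts two measures under its primary-outcomes heading. The first is HbA1c: "HbA1c is an established measure of diabetes control and a strong predictor of subsequent health outcomes related to diabetes". The second is the DDS: "DDS, a 17-item instrument that assesses psychological burden specific to diabetes care". Neither is ranked above the other, and that section names no primary time point.

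The hypotheses in sections 0.0.2 and 3.0 split H2 (post-intervention) and H3 (after the maintenance period) into part a for HbA1c and part b for DDS. Section 5.6.C.i, labelled effectiveness, specifies separate ANCOVAs: "one with HbA1c at post-intervention as the outcome and one with DDS at post-intervention as the outcome". Section 5.6.C.ii, labelled maintenance, repeats this later: "one with HbA1c at 10-months as the outcome and one with DDS at 10-months as the outcome". The H3 models adjust for "respective HbA1c and DDS post-intervention scores" rather than for baseline.

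On error control, section 5.6.A says only: "All tests will be two-sided with an alpha of 0.05". It sizes the trial on the post-intervention effect, with d = 0.40 chosen to serve both outcomes. The document contains no hierarchy, alpha split, gatekeeping or rule that both outcomes must succeed.

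**The concern.** Specific Aim 2 asks one question: is EPIC more effective than enhanced usual care? Two primary tests answer it, each at 0.05, and the plan does not say what pattern of results counts as a yes. A trial with no effect on HbA1c and p = 0.04 on DDS could be reported as positive on a primary outcome, and so could the reverse. The 5% in the plan is then the error rate of each test, not of the effectiveness claim. The sample size makes no allowance for this. Without a rule fixed in advance, the choice of which result carries the conclusion can be made after the results are known.

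**Working it through.** **Inputs from section 5.6.A:** two-sided alpha 0.05 per test; d = 0.40; 100 per arm before inflation; ICC 0.0183 with 12 patients per PACT; 15% attrition; 142 per arm, 284 in total. **Assumed:** correlation between the two outcomes of 0 to 0.5. Section 5.1.I.b says they correlate but gives no figure.

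**1. The plan's own figure.** n per arm = 2(1.960 + 0.842)²/0.40² = 98.1, so 99 (stated: 100). The design effect is 1 + 11 × 0.0183 = 1.2013; 100 × 1.2013 = 120; 120/0.85 = 141.2, so 142 per arm and 284 in total. This reproduces. Power with an effective 100 per arm is Φ(0.40 × √50 − 1.960) = Φ(0.868) = 80.7%. The whole calculation is for a single test at 0.05.

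**2. Two post-intervention tests, either suffices, no true effect.** If independent: 1 − 0.95² = 9.75%. By bivariate normal simulation:

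| Outcome correlation | Family-wise error |
|---|---|
| 0 | 9.8% |
| 0.3 | 9.5% |
| 0.5 | 9.1% |

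**3. Both required.** The false-claim rate cannot exceed 5%. Joint power at d = 0.40 on both outcomes is 0.807² = 65% if independent, and 70% at correlation 0.5.

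**4. All four tests in one family.** If independent: 1 − 0.95⁴ = 18.5%. The plan's own models were simulated under no effect: H2 adjusted for baseline, H3 adjusted for the post-intervention score, 120 per arm, 10,000 runs per setting, within-outcome correlation over time 0.5 to 0.7, between-outcome correlation 0 to 0.5. The rate is 16.9% to 18.6%, and the H2 and H3 statistics for HbA1c correlate at about −0.16 to −0.30. Using baseline as the H3 covariate instead gives 17.0% to 18.6%, so the rate does not hinge on that choice.

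**5. Holm on the post-intervention pair** (smaller p-value against 0.025, then the larger against 0.05). Power per outcome at d = 0.40, effective 100 per arm:
- both effects real: 78.3% at correlation 0, 77.3% at correlation 0.5;
- only one real: about Φ(2.828 − 2.241) = Φ(0.587) = 72%.

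**6. Fixed sequence, HbA1c then DDS.** HbA1c keeps its 80.7%. A confirmatory DDS claim needs both tests significant, so its chance is the joint power in step 3, about 65–70%.

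**The case against.** The strongest reply is that H2a and H2b are separate hypotheses. Each has a 5% error rate, and whether to control error across them is partly convention. This stands if the two results are only ever reported as two separate claims. It does not stand for a single statement that EPIC is effective, and that is how Aim 2 and the effectiveness row of Table 5 (section 5.5.A) frame the pair.

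A second reply is that both outcomes may be meant to succeed, in which case having two causes no inflation. That is correct, but no section says so, and the planned 80% would then not be the power of the trial.

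A reader might also infer that there are four primary tests, any one of which could be reported as primary effectiveness. The documents do not support that as fact. Table 5 defines effectiveness by the 4-month differences and maintenance by the 10-month ones; sections 5.6.C.i and 5.6.C.ii use the same labels; and the sample size rests on the post-intervention effect. They do not rule it out either: no section names post-intervention as the sole primary time point, H3 is a stated hypothesis with its own power claim, and only the analyses in 5.6.C.iii and the implementation associations are called exploratory.

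Finally, any multiplicity rule has a price. Section 5.6.A aimed to capture both outcomes and claims 80% power at the later follow-up, and those powers would not all survive. This stands, so the cost belongs with the fix.

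**Conclusion.** The gap is real: two unranked primary outcomes, each tested at 0.05 post-intervention, with no success rule and no multiplicity control. If either result suffices, the family-wise error is about 9–10%, or 1.8 to 1.95 times the stated 5%. That depends on the either-suffices reading and on an assumed outcome correlation of 0 to 0.5. Under a both-required reading the error is not inflated, and the problem becomes power of about 65–70% at d = 0.40. The plan must choose in either case.

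The 17–19% figure for four tests applies only if the 10-month tests belong to the same family, which the documents leave unclear. A reader might reach a somewhat lower four-test rate, 15.6% to 17.3%, by assuming test statistics correlated +0.5 to +0.7 over time (outcome correlation 0 to 0.3). The plan's H3 models do not produce such correlations. None of this invalidates the trial; it leaves the error rate of its main claim undefined.

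**What to change.** In sections 5.6.A and 5.6.C, state that the two H2 tests form the primary family, controlled at two-sided 0.05 by one of two rules:

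- **Holm** across HbA1c and DDS; or
- **a fixed sequence** with HbA1c first, and DDS tested only if HbA1c is significant.

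State that the H3 tests are secondary and are tested only after H2 under the same rule. With Holm, open the H3 pair at 0.05 only if both H2 tests are rejected; with the sequence, continue in the stated order. If the intent is that both outcomes must succeed, say that instead and quote the joint power.

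**Cost.** The wording changes and no patients are added, but the power statement must change too. Holm lowers per-outcome power at d = 0.40 from about 81% to 77–78% if both effects are real, and to about 72% if only one is. The fixed sequence keeps the planned power for HbA1c, but the chance of a confirmatory post-intervention DDS claim is about 65–70%, and later claims are less likely still. Under either rule, a failed DDS test post-intervention can block a confirmatory HbA1c claim at 10 months. For scale, 80% power at 0.025 per outcome would need 119 per arm before inflation: 119 × 1.2013 = 143, and 143/0.85 gives 169 per arm, 338 in total.

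The sponsor should choose between the two rules before unblinding and restate the power to match.

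### The 98% power stated for 100 patients per arm at d = 0.50 should be 94%; N = 284 is unaffected

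*Combined protocol and SAP*

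**What the plan says.** Section 5.6.A sets the error rate: "All tests will be two-sided with an alpha of 0.05". It takes d = 0.40 as the planning effect and assumes at first no correlation within PACTs. On that basis it states that 100 patients per arm "will allow for 80% power to detect small-to-medium effects and 98% power to detect medium effects", with d = 0.50 given as the medium effect. It then multiplies the 100 by a design effect of 1.2013 to reach 120, and adds attrition: "Further adjusting for a maximum of 15% attrition, 142 patients will be recruited for each treatment group", 284 in total.

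The section also covers power for "linear change across the three time points for a 3-level cluster-randomized trial with repeated assessments". It asserts: "A sample size of 284 participants is adequate for repeated measures analyses as well". From prior data it takes a difference in linear HbA1c change of 0.20, with slope variances of 0.018 between PACTs and 0.206 within them, and concludes: "These values indicate a small-to-medium between-groups effect size of 0.42". Power is then given at two other effects. The first statement is "A total of 284 participants allows for 80% power to detect a slightly larger effect size", namely 0.53. The second is 98% power at 0.75.

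Sections 5.1.A and 5.1.D.iv randomize individual patients. Section 5.6.A itself describes "an average of approximately 12 patients randomized to either EPIC or EUC from within 24 PACTs sampled". Section 5.1.B uses both the cluster and the patient-level description in one sentence. Section 5.6.C.iii places the growth-curve analysis among the exploratory analyses. H2 and H3 use ANCOVA (5.6.C.i and 5.6.C.ii).

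**The concern.** The two powers in one sentence share a sample size, an alpha and a no-clustering assumption, so they should come from a single formula. They do not: moving from d = 0.40 to d = 0.50 at 100 per arm does not lift power from 80% to 98%. At stake is the accuracy of a printed figure that any reader can check and that could be carried into a methods section. A wrong figure beside a right one also invites doubt about the calculation that does set N.

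The wording point is narrower. Calling 284 adequate for the repeated-measures analysis rests on 80% power at 0.53, which is 26% above the 0.42 that the section derives (0.53 / 0.42 = 1.26), and on a design described differently from the one the trial uses. No power is stated at 0.42.

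**Working it through.** **Inputs, all from section 5.6.A.** Two-sided alpha 0.05; 100 per arm; ICC 0; standardized effects (SD = 1) of d = 0.40 and d = 0.50.

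**Formula.** Noncentrality = d × √(n/2) = d × √50 = 7.071d. Normal-approximation power = Φ(noncentrality − 1.960). The noncentral t uses 198 degrees of freedom.

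| d | Noncentrality | Normal | Noncentral t | Stated |
|---|---|---|---|---|
| 0.40 | 2.828 | Φ(0.868) = 80.7% | 80.4% | 80% |
| 0.50 | 3.536 | Φ(1.576) = 94.2% | 94.0% | 98% |

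The first row reproduces and the second does not. At d = 0.50, 98% would need 2 × (1.960 + 2.054)² / 0.50² = 129 per arm (130 by the t calculation). At 100 per arm it would need d of about 0.57.

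**Could another reading give both figures?**

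| Reading | d = 0.40 | d = 0.50 |
|---|---|---|
| One-sided 0.05, 100 per arm | 88.0% | 97.0% |
| Baseline adjustment strong enough for 98% (r about 0.47), 100 per arm | 89% | 98% |
| 120 per arm, no ICC | 87.0% | 97.1% |
| 142 per arm, no ICC | 91.9% | 98.7% |

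None returns 80% and 98% together. The one-sided reading also contradicts the stated alpha, and the last two do not use the stated 100.

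**Does N depend on the 98%?** Design effect = 1 + (12 − 1) × 0.0183 = 1.2013. Then 100 × 1.2013 = 120; 120 / 0.85 = 141.2, rounded up to 142; 2 × 142 = 284. Every step starts from the 100 that gives 80% at d = 0.40.

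**The repeated-measures wording.** The prior-data effect reproduces: 0.20 / √(0.018 + 0.206) = 0.423. Power at that effect can only be back-solved from the stated 80% at 0.53, and the answer depends on the assumed design:

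- *Scaling the stated anchor on its own cluster-randomized basis.* (1.960 + 0.842) × 0.42 / 0.53 = 2.220, and Φ(2.220 − 1.960) = 60%. The same scaling gives 97.7% at 0.75, consistent with the stated 98%.
- *Patient-level randomization, PACT slopes fully shared by both arms, all 284 contributing.* The stated 80% at 0.53 implies a contrast variance of 0.0080 (normal) or 0.0073 (t, 22 df). Removing the between-PACT term, 4 × 0.018 / 24 = 0.0030, leaves 0.0050 or 0.0043. For a slope difference of 0.20, power is Φ(0.20/√0.0050 − 1.960) = 81% or Φ(0.20/√0.0043 − 1.960) = 86%.

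The second case assumes equal allocation and 24 equal PACTs. Dividing the remainder by 0.85 for attrition, which assumes that dropouts add no slope information, brings it to about 74–80%. Treatment-by-PACT variation or dependency within EPIC groups would lower it further, but the documents give no values for either.

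**The case against.** On the 98%, the best defence is that it is an aside. It feeds no later step, and with no ICC the larger numbers of 120 and 142 per arm give 97.1% and 98.7%, so the printed value is close to what a bigger sample would deliver. That limits the consequence but does not rescue the sentence, which ties the figure to 100 per arm.

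On the wording note, more of the defence stands. Section 5.6.A prints both 0.42 and 0.53, so nothing is concealed, and *slightly larger* is a matter of adjective. The analysis is exploratory. The 0.42 comes from a trial of EPIC against enhanced group education, whereas the comparator here is enhanced usual care: a referral, a packet and a letter. It is therefore a prior-data effect, not a declared expectation for this trial.

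A reader might infer that the growth-curve analysis is underpowered, with about 60% power at 0.42. The documents do not support that. The 60% keeps the cluster-randomized basis; with patient-level randomization and shared PACT slopes, the same anchor gives about 81–86%. The section omits software inputs needed to choose between them, such as the patient-level error variance.

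**Conclusion.** The stated 98% is wrong on the plan's own inputs: it should be 94%, an overstatement of about 4 points. This rests only on the printed n, alpha, effect size and zero ICC, and confidence is high. Severity is minor.

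A reader might infer that the trial is undersized. It is not shown to be: the 80% at d = 0.40 reproduces, and so does the chain to 284. Nor does the error establish the power of the final sample at d = 0.50, which depends on how much of the design effect applies when both arms are drawn from the same PACTs.

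The repeated-measures point is one of unsupported wording, not arithmetic. The section shows 80% power at 0.53 under a cluster-randomized description and nothing at 0.42. Back-solved values run from roughly 60% to 86% depending on assumptions, so the text supports neither adequacy nor inadequacy at that effect. The ANCOVA analyses for H2 and H3 are untouched by this note.

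**What to change.** In section 5.6.A, replace 98% with 94% for 100 patients per arm at d = 0.50.

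In the repeated-measures sentences, drop the claim of adequacy and state that 284 patients give 80% power at an effect of 0.53 under a cluster-randomized assumption. Do not add a power figure at 0.42, and do not print the back-solved values above.

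The cost is one number and one reworded sentence. No patients are added, no analysis changes, and no software calculation has to be re-run.
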